Only substantial protocol deviations with the potential to significantly affect the study results or to invalidate the interpretation of the data obtained will lead to exclusion of patients from the PP set. The membership of each patient in the respective analysis populations will be determined before statistical analysis in a data review meeting by a panel consisting of a medical expert from the Sponsor, the clinical study manager, the data manager, and the study statistician.

Name of Sponsor/Company: Octapharma USA, [name]	
Name of Investigational Product: CUTAQUIG	Protocol Identification Code: SCGAM-06
Name of Active Ingredient: Human Normal Immunoglobulin	Date of Final Protocol: 28-Aug-2019

In the event that a patient is not treated according to the dosing regimen described for their assigned cohort, the original cohort assignment will still be used for Safety and ITT analyses (SAF and FAS populations). These patients will be removed from the PP population due to protocol violations.

Statistical Analysis Plan:

A formal statistical analysis plan describing all details of the analyses to be performed will be prepared by the study statistician and approved by the Sponsor prior to start of the statistical analysis.

The safety analysis will comprise descriptive statistics, tabulations and listings of all TEAEs, safety laboratory results, vital signs and physical examination findings. All reported AEs will be coded according to the Medical Dictionary for Regulatory Activities (MedDRA).

For each TEAE, the time relative to the start of the infusion will be calculated and the TEAE will be classified as temporally associated if the onset is during the infusion or within 72 hours after the end of the infusion.

All reported AEs will be listed and tabulated in full detail, in particular the following key figures will be presented for each cohort and for the study as a whole:

- Total number of TEAEs reported in the Stabilization and Treatment Periods
- Number of TEAEs temporally associated with CUTAQUIG delivered during the Treatment Period
- Number of TEAEs temporally associated with CUTAQUIG delivered during the Stabilization Period
- Infusion rate at the onset of temporally associated TEAEs (frequencies and percentages)
- Narratives will be prepared describing each death, other serious adverse events (SAEs), and other significant AEs that are judged to be of special interest because of clinical importance.

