3 INVESTIGATIONAL PLAN

3.1 Primary and Secondary Endpoints

3.1.1 Primary Endpoints

There is no single primary endpoint in this study. The co-primary objectives are to compare total IgG trough levels from weekly infusions to every other week infusions and to assess safety and tolerability of increased infusion volumes and increased infusion rates at each infusion site and every other week dosing. These will be assessed using the following variables:

- Change in individual total IgG trough levels from weekly infusions to every other week infusions (Cohort 3)
- Occurrence of treatment-emergent AEs (TEAEs) throughout the entire Stabilization and Treatment Periods starting with the first infusion of IMP
- Occurrence of TEAEs temporally associated with CUTAQUIG delivered during the Treatment Period
- Occurrence of TEAEs temporally associated with CUTAQUIG delivered during the Stabilization Period
- TEAEs by speed of infusion
- Local infusion-site reactions
- Laboratory parameters (hematology, clinical chemistry, urinalysis)

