9.2.3.1 Adverse Events

All reported AEs will be coded according to the Medical Dictionary for Regulatory Activities (MedDRA).

An AE is defined as treatment-emergent if first onset or worsening is after start of the first infusion of CUTAQUIG. Only TEAEs are accounted for in the analysis.

Any untoward medical events that occur between informed consent and the start of the first infusion of CUTAQUIG will be considered pre-treatment AEs. These events will not be entered into the safety database as they are not TEAE.

For each TEAE, the time relative to the start of the infusion will be calculated and the TEAE will be classified as temporally associated if the onset time is during the infusion or within 72 hours after the end of the infusion.

All reported AEs will be listed and tabulated in full detail, in particular the following data will be presented:

- Total number of TEAEs reported
- Number of TEAEs
- Infusion rate at the onset of TEAEs
- Narratives will be prepared describing each death, other SAEs, and other significant AEs that are judged to be of special interest because of clinical importance

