7. General Issues for Statistical Analysis

Descriptive summaries will be presented for each of the primary and secondary variables. In general, summaries will be completed for all patients overall and by study cohort if applicable.

Continuous, quantitative variable summaries will in general include the number of patients with non-missing values (N), mean, standard deviation, median, minimum and maximum, 1st and 3rd quartile.

Categorical, qualitative variable summaries will include the frequency and percentage of patients who are in the particular category. In general the denominator for the percentage calculation will be based upon the total number of patients in the analysis population unless otherwise specified.

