$$\left[e^{\ln(r) - 2.33 \cdot \sqrt{\frac{\sum C_i^2}{C^2}}} ; e^{\ln(r) + 2.33 \cdot \sqrt{\frac{\sum C_i^2}{C^2}}} \right]$$

If there are 0 infections, an alternative method will be used to approximate the upper bound on the 98% confidence interval using a chi-square distribution and the following SAS code:

```
data poisson;
events=0;
sumyrs=xxx;
ul=cinv(0.99,2*(events+1))/2;
rate=events/sumyrs;
ulinc=ul/sumyrs;
run;
where
sumyrs = duration of treatment in years
events = total number of events
```

rate = total number of events per person-year

ulinc = two-sided 98% CI - upper limit

- The **rate of infusions with one or more temporally associated AEs** will be calculated for each patient as $r = (\text{Number of infusions with one or more temporally associated AEs}) / (\text{Number of infusions started})$. An AE is defined as a temporally associated if, and only if, the onset (or worsening) is either during an infusion of study medication or within 72 hours of the end of the infusion. [Unit: N/A]

Property of Octapharma. Do not copy or distribute without written permission.

8. Study Subjects and Demographics

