10.1. Adverse Events

All reported AEs will be coded according to MedDRA.

An AE is defined as treatment-emergent, if first onset or worsening is after start of the first infusion of CUTAQUIG. Only treatment-emergent AEs (TEAEs) are accounted for in the analysis.

For each TEAE, the time relative to the start of the infusion will be calculated and the TEAE will be classified as temporally associated if the onset is during the infusion or within 72 hours after the end of the infusion.

All reported events will be listed and tabulated in full detail; in particular the following key statistics will be presented in a summary table:

- Total number of TEAEs reported.

Number of patients with

- Any TEAE
- Any drug related TEAE
- Any TEAE
- Any Drug Related TEAE
- Any Temporally Associated TEAE during Stabilization Period
- Any Temporally Associated TEAE during Treatment Period
- Any Local Site Reaction
- Any Severe TEAE
- Any Serious AE
- Product Withdrawn due to TEAE
- Study Discontinuation due to TEAE
- AE Outcome of Death

Also, the following TEAE tabulations of patient incidence will be presented:

- Temporally associated treatment-emergent adverse events during stabilization period by system organ class and preferred term
- Temporally associated treatment-emergent adverse events during treatment period by system organ class and preferred term
- Local site reaction treatment-emergent adverse events by system organ class and preferred term
- Treatment-emergent adverse events excluding local site reactions by system organ class and preferred term
- Serious treatment-emergent adverse events by system organ class and preferred term
- Serious treatment-emergent adverse events leading to study discontinuation by system organ class and preferred term
- Non-serious treatment-emergent adverse events by system organ class and preferred term
- Treatment-emergent adverse events leading to product withdrawal by system organ class and preferred term

- Treatment-emergent adverse events leading to early study discontinuation by system organ class and preferred term
- Treatment-emergent adverse events by highest relationship to treatment by system organ class and preferred term
- Treatment-emergent adverse events by maximum severity by system organ class and preferred term
- Infusion total flow rate and temporally associated treatment-emergent adverse events

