- Infusion total flow rate associated with temporally related treatment-emergent adverse events- non-local site reactions
- Infusion total flow rate associated with temporally related treatment-emergent adverse events- local site reactions only
- Infusion total flow rate/number of lines associated with temporally related treatment-emergent adverse events- local site reactions only
- Percentage of infusions with one or more temporally associated TEAE

The following table listings of interest will be presented:

- Table listing of serious treatment-emergent adverse events
- Table listing of related treatment-emergent adverse events
- Table listing of related serious treatment-emergent adverse events
- Table listing of treatment-emergent adverse events leading to death
- Table listing of treatment emergent adverse events leading to study drug discontinuation
- Table listing of treatment-emergent adverse events leading to study discontinuation
- Table listing of local site reactions
- Table listing of treatment-emergent incidences of fever safety

Further, all AE data collected, including the infusion rate at onset of TEAE will be presented in by-patient listings.

Narratives will be prepared describing each death, other SAEs, and other significant AEs that are judged to be of special interest because of clinical importance

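### The planned tables for the co-primary adverse-events-by-speed variable commit to no count of infusions given at each speed, so event percentages largely track exposure

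*Protocol*

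**What the plan says.** Protocol 3.1.1 and SAP 3.2.1 both list "TEAEs by speed of infusion" among the co-primary variables.

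- **Protocol.** The Study Outline's key safety figures include "Infusion rate at the onset of temporally associated TEAEs (frequencies and percentages". Protocol 9.2.3.1 has only "Infusion rate at the onset of TEAEs", without the restriction to temporally associated events. An event is temporally associated if it starts during an infusion or up to 72 hours after its end.
- **SAP 10.1, flow-rate tables.** The list is introduced by "Also, the following TEAE tabulations of patient incidence will be presented". The first flow-rate table is "Infusion total flow rate and temporally associated treatment-emergent adverse events". Two more use total flow rate, one for non-local and one for local reactions. The fourth is "Infusion total flow rate/number of lines associated with temporally related treatment-emergent adverse events- local site reactions only". Only titles are given: no speed bands and no denominators.
- **SAP 7, default denominator.** "In general the denominator for the percentage calculation will be based upon the total number of patients in the analysis population unless otherwise specified".
- **SAP 7.4, 10.1 and 10.2, infusion-based measures.** Infusions with a temporally associated event are divided by all infusions. None of these measures is broken down by speed.
- **SAP 8.4.** Flow rates are summarized as compliance data, unbanded and not linked to events.
- **SAP 2 and 13.** The detailed list of tables is left to a later, separate document.

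**The concern.** A percentage of events at a given rate depends on two things: the risk per infusion at that rate, and how many infusions were given at it. Without the second, the first cannot be read off the table.

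In Cohort 2 the exposure is very uneven by design. Each step lasts four weekly infusions, and a patient who reaches the ceiling stays there for the rest of the 24 weeks. If most patients escalate fully, the top rate collects many events simply because it was used most. If few do, the top rate shows few events because it was rarely used. A table built to describe tolerability by speed could mislead in either direction.

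Two definitional gaps add to this. An event that starts after the infusion has ended has no infusion rate at onset, and neither document says that the preceding infusion's rate applies. Total flow rate also mixes per-site speed with the number of sites.

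**Working it through.** The plan states no figure for this variable, so there is nothing to reproduce. The check is a search for a per-speed denominator, followed by an illustration.

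**Search.** The sections cited above contain no count of infusions per speed band and no event percentage per infusion at each speed.

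**Inputs from the documents.** Four stabilization infusions at the prior rate; weekly infusions at Weeks 0 to 24, which is 25; steps of up to 25 mL/hr/site for patients of at least 40 kg; four infusions per step; a ceiling of 100 mL/hr/site (Protocol 3.3.2 and 5.5.3); at least 15 patients in Cohort 2.

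**Assumptions.** The documents give no starting rate; take 20 mL/hr/site, with every full step tolerated.

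**Formula.** With n_k infusions at rate k and risk r_k per infusion, the share of events at k is n_k·r_k / Σ(n_j·r_j). Total infusions: 4 + 4 + 4 + 4 + 13 = 29.

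| Rate (mL/hr/site) | Infusions | Equal risk | Top-rate risk halved | Top-rate risk doubled |
|---|---|---|---|---|
| 20, 45, 70, 95 (each) | 4 | 4/29 = 13.8% | 4/22.5 = 17.8% | 4/42 = 9.5% |
| 100 | 13 | 13/29 = 44.8% | 6.5/22.5 = 28.9% | 26/42 = 61.9% |

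The top rate holds the largest share of events even when its risk per infusion is half that of the others. Dividing the events at k by n_k removes the exposure and leaves r_k.

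**Sensitivity, equal risk throughout.**
- Start at 15: 13/29 = 44.8% of events at 100. Start at 25: 17/29 = 58.6%. Start at 50: 21/29 = 72.4%.
- Start at 20 with only 5 of 15 patients reaching 100: (5 × 13)/(15 × 29) = 65/435 = 14.9%.
- Patients under 40 kg, steps of 10, start at 10 or 20: the highest rate reached (70 or 80) has 5/29 = 17.2%.

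**Combined-rate limit.** Protocol 5.5.3 caps all sites together at 240 mL/hr. Two sites at 100 give 200, which is allowed. Three equal sites reach at most 240/3 = 80 each. The path to 100 therefore applies to patients using one or two sites.

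**Total against per-site rate.** Two sites at 50 and four sites at 25 both give 100 mL/hr in total, yet the per-site speed differs twofold. Only the fourth SAP table separates them, and it covers local reactions only.

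**Can each event be assigned to one infusion?** Protocol 5.4 sets at least 4 days, or 96 hours, between infusions. The 72-hour windows cannot overlap unless an infusion lasts more than 96 − 72 = 24 hours.

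**The case against.** The strongest reply is that the SAP tables are titles only and their layouts are deferred. The heading about patient incidence does not settle the denominator either, since the same list ends with a percentage of infusions. That stands: one cannot say that the SAP tables will divide by patients, only that the SAP commits to no per-speed infusion count. A patient denominator would not help in any case, because a patient with 13 infusions at a rate has more chances of an event there than one with four. SAP 7.4 also allows further derivations for primary variables to be described only in the study report, so the choice could be made after the data are seen.

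Flow-rate exposure will also be summarized under SAP 8.4. This gives some context, but as written a reader could not match events to exposure at each speed.

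Two stronger readings are tempting and are not supported:
- **That rate at onset is undefined for most qualifying events.** For an assumed 1- to 2-hour infusion, 72/73 = 98.6% to 72/74 = 97.3% of the window lies after the infusion. That is a share of hours, not of events, and nothing in the documents says that onsets spread evenly. The SAP titles that speak of flow rate associated with events may also intend a link to the preceding infusion.
- **That the Cohort 2 co-primary question goes unanswered.** Safety at increased flow rates is assessed by several variables. They include temporally associated events reported separately for the Stabilization Period, at the prior rate, and the Treatment Period.

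Finally, a denominator does not make the comparison causal. Rates rise only when earlier infusions were tolerated, patients may step back after reactions, and cohort choice follows preference.

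**Conclusion.** The point holds for this one co-primary variable. The protocol specifies an event-only distribution, and the SAP does not commit to the infusion counts needed to interpret it. With no effect of speed at all, the illustrations put between 14.9% and 72.4% of events at 100 mL/hr/site, depending only on starting rate and on how many patients escalate. These figures rest on assumed starting rates and escalation patterns, so they show the mechanism and do not forecast the result. The post-infusion definition gap and the mismatch between total and per-site rate are real but secondary. The weakness lies in the planned tabulation and not in the data, since infusion speed is recorded (Protocol 5.7.2 and 8.1.1). It should be corrected, but it does not undermine the rest of the safety description.

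**What to change.** In SAP 10.1:

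1. Assign each temporally associated TEAE to the infusion during or after which it starts.
2. Classify each infusion by its maximum flow rate per site, in bands fixed before the tables are run, and keep total flow rate as a supplement. Using the maximum prevents an event from moving to a lower band when the rate was cut because of it.
3. For each band report infusions given, infusions with at least one temporally associated TEAE, and the percentage with a confidence interval clustered by patient. SAP 10.2 already accepts the need to allow for intra-patient correlation.
4. Present this by cohort and separately for local and non-local events, with a note that the comparison is descriptive.

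The cost is SAP wording and one more table, with no new data collection. The downside is sparse cells and wide intervals in small cohorts, which argues for few bands.

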15 APPENDICES	87

TABLE OF TABLES

Table 1: Screening and Stabilization Periods – Flow Chart of Assessments	17
Table 2 Cohort 1 (Increased Volume) – Flow Chart of Assessments	18
Table 3: Cohort 2 (Increased Infusion Rate) – Flow Chart of Assessments	19
Table 4: Cohort 3 (Every Other Week Dosing) – Flow Chart of Assessments	20
Table 5: Biochemical Characteristics of CUTAQUIG	49
Table 6: Infusion Volume and Flow Rate by Patient Weight	52
Table 7: Study Visit Times and Windows Used in this Study	57
Table 8: Diagnostic Criteria for Serious Bacterial Infection Types	61
Table 9: Laboratory Tests and Time Points	68

Property of Octapharma. Do not copy or distribute without written permission.

LIST OF ABBREVIATIONS

Abbreviation	Description
ADR	Adverse drug reaction
AE	Adverse event
ALT	Alanine aminotransferase
AST	Aspartate aminotransferase
AUC	Area under the concentration–time curve
BL	Baseline
BMI	Body mass index
Cmax	Maximum concentration of drug
Cmin	Minimum concentration of drug
CRO	Contract research organization
CSF	Cerebrospinal fluid
eCRF	Electronic Case Report Form
EDC	Electronic data capture
FAS	Full analysis set
FDA	Food and Drug Administration
GCP	Good Clinical Practice
HCV	Hepatitis C virus
HIV	Human immunodeficiency virus
IDMC	Independent Data Monitoring Committee
IgA	Immunoglobulin A
IgG	Immunoglobulin G
IMP	Investigational medicinal product
IRB	Institutional Review Board
IV	Intravenous
IVIG	Intravenously administered immunoglobulin
LDH	Lactate dehydrogenase
MedDRA	Medical Dictionary for Regulatory Activities
NAT	Nucleic acid testing
PI	Primary immunodeficiency
PK	Pharmacokinetic(s)
PP	Per protocol
QoL	Quality of life
SAE	Serious adverse event
SBI	Serious bacterial infection
SC	Subcutaneous
SCIG	Subcutaneously administered immunoglobulin
SF-10	Short Form Health Survey, 10 item
SF-36	Short Form Health Survey, 36 item
TEAE	Treatment-emergent adverse event
TEE	Thromboembolic event
Tmax	Time to maximum plasma concentration
WBC	White blood cell

GLOSSARY OF TERMS

Term	Definition
Treatment Period Baseline	The first visit during the Treatment Period
CUTAQUIG-naïve patients	Patients who did not participate in Study SCGAM-03
Cohort 1 (increased volume)	This cohort will evaluate the safety and tolerability of CUTAQUIG delivered at increased volume per site than delivered with previous SCIG treatments. During the Stabilization Period, patients will receive CUTAQUIG at the same body-weight dependent (mg/kg) dose and infusion flow rate as their previous SCIG product; however, this flow rate should not exceed maximum infusion rates listed in protocol. During the Treatment Period, patients will return to the clinic at Baseline to receive their first dose of CUTAQUIG with an infusion volume increase of up to the maximum allowed volume increase per infusion site of 25 mL/site for patients ≥ 40 kg or 10 mL/site for patients < 40 kg. Every 4 weeks the infusion volume will be increased again by up to 25 mL/site or 10 mL/site for patients < 40 kg until reaching a maximum dose (in mL), or maximum tolerated volume (maximum volume based on Investigator's decision of patient's tolerance), or 100 mL at 1 injection site – whichever is reached first.
Cohort 2 (increased flow rate)	This cohort will evaluate the safety and tolerability of CUTAQUIG delivered at increased flow rates than those delivered with previous SCIG treatments. During the Stabilization Period, patients will receive CUTAQUIG at the same body-weight dependent (mg/kg) dose and infusion flow rate as their previous SCIG product; however, this flow rate should not exceed maximum infusion rates listed in protocol. During the Treatment Period, patients will return to the clinic at Baseline to receive their first dose of CUTAQUIG with an infusion rate increase up to a maximum allowed flow rate increase per infusion site of 25 mL/hr/site for patients ≥ 40 kg or 10 mL/hr/site for patients < 40 kg. Every 4 weeks the infusion flow rates will be increased again by up to 25 mL/hr/site for patients ≥ 40 kg or 10 mL/hr/site for patients < 40 kg until either 1) a maximum flow rate (100 mL/hr/site) or the maximum flow rate achievable by the pump, or 2) the maximum tolerated flow rate (based on Investigator's decision of patient's tolerance) – whichever is reached first.
Cohort 3 (every other week dosing)	This cohort will evaluate the safety and tolerability of CUTAQUIG delivered at the same or equivalent of twice the weekly mg/kg dose administered every other week with previous SCIG treatment. During the Stabilization Period, patients will receive CUTAQUIG at the same body-weight dependent (mg/kg) dose and infusion flow rate as their previous SCIG product; however, this flow rate must not exceed maximum infusion rates listed in protocol. During the Treatment Period, patients will return to the clinic at Baseline to receive their first double mg/kg weekly dose and begin an every other week dosing schedule. When switching from weekly to every other week dosing, infusion volume increases per site must not exceed a maximum allowed volume increase per infusion site of 25 mL/site for patients ≥ 40 kg or 10 mL/site for patients < 40 kg at the Treatment Period Baseline Visit. If a patient's doubling of their weekly dose requires dosing with a volume of more than the maximum allowed volume increase per injection site (25 mL/site or 10 mL/site, dependent on patient body weight), they will be required to increase the number of infusion sites to remain below the maximum body-weight dependent volume increase. If this occurs, after 2 infusions the patient may remove 1 of the newly introduced injection sites as long as the volume per injection site increase limit is not exceeded.
CUTAQUIG	Immune Globulin Subcutaneous (Human). BLA approval received December 12, 2018 by US FDA.
Enrolled	Patients will be considered enrolled into the study after written informed consent (and assent, if age-appropriate) has been obtained.
Infusion site	An anatomical location of IMP infusion.

Term	Definition
Stabilization Period	Patients will receive CUTAQUIG infusions at the same body-weight dependent (mg/kg) dose and infusion flow rate (ml/hr/site) as their previous SCIG product; however, this flow rate should not exceed maximum infusion rates listed in protocol. Patients entering the study currently active and established on CUTAQUIG in Study SCGAM-03 will have already been stabilized on CUTAQUIG and will proceed directly into the Treatment Period following completion of Screening. All other patients, including patients who completed their participation in Study SCGAM-03 and went on a commercial SCIG product prior to the Screening Visit, will need to complete the Stabilization Period
Treatment Period	Patient will receive CUTAQUIG infusions according their assigned cohort parameters.

Property of Octapharma. Do not copy or distribute without written permission.

